10.6.2.2. Hematologic Improvement

Hematological improvement as measured by change from baseline hemoglobin level will be summarized by treatment arms. The percentage of subjects with sustained hematological improvement as measured by change from baseline in hemoglobin level will be presented and compared using a chi-square test. The distribution of the time to improvement in hemoglobin will be summarized using Kaplan-Meier estimates and time to improvement will be compared using stratified or unstratified log-rank test as appropriate.

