1.1. Study Design

This is a randomized, placebo-controlled, double-blind, Phase 3 study designed to evaluate whether treatment with ibrutinib in combination with rituximab will result in an improvement in progression-free survival (PFS) compared to placebo in combination with rituximab in subjects with WM (untreated and previously treated). In addition, an open-label ibrutinib substudy is included to further investigate the safety and efficacy of ibrutinib monotherapy in subjects with WM who are considered refractory to the last prior rituximab-containing therapy.

A total of 150 subjects were randomized in a 1:1 ratio to receive ibrutinib and rituximab (Treatment Arm A) or placebo and rituximab (Treatment Arm B). 31 subjects were enrolled in the open-label ibrutinib monotherapy substudy (Treatment Arm C). All subjects in Arm A and Arm B are to receive intravenous rituximab 375 mg/m² once weekly for 4 consecutive weeks, followed by a second 4-weekly rituximab course after a 3-month interval. In addition, all subjects in Arm A and Arm B, per randomization, are to receive oral study drug (420 mg ibrutinib or matching placebo), administered once daily and continuously until criteria for permanent discontinuation of study drug are met. All subjects in Arm C are to receive oral ibrutinib 420 mg, administered once daily and continuously until criteria for permanent discontinuation of study drug are met.

The study includes a Screening Phase, Treatment Phase and a Follow-Up Phase. All subjects are to be followed for disease progression until a PFS event occurs or until the data cutoff for final analysis.

Access to ibrutinib (cross-over) as next-line therapy for subjects with Independent Review Committee (IRC) confirmed disease progression and treated with placebo in combination with rituximab (Arm B) are provided as outlined in the protocol. Subjects who have symptomatic disease meeting criteria for requiring treatment may be eligible to receive ibrutinib as next-line therapy.

An IRC has been established to conduct response assessment and evaluate disease progression status centrally per the IRC charter.

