1.6. Testing Procedure and Level of Significance

Interim Analysis

In order to preserve the study wise 2-sided type I error rate of 0.05, the 2-sided significance level for PFS will be 0.015 at 50 PFS events for the interim analysis, based on O'Brien Fleming boundary. However, the alpha spending for PFS will be determined based on the actual information fraction using O'Brien-Fleming boundary at the time of the interim analysis.

If the primary endpoint achieves statistical significance, tests of secondary endpoints will be performed at the 2-sided significance level of 0.05 in a sequential hierarchical manner based on a closed testing procedure. The secondary endpoints will be ranked in sequence according to the hierarchical order specified below. OS will not be tested at interim analysis and will be tested at study closure.

- 1.) ORR
- 2.) TTnT
- 3.) Rate of sustained hemoglobin improvement
- 4.) Proportion of subjects with \geq 3 points increase from baseline by Week 25 in fatigue experience score
- 5.) OS

Final Analysis

The 2-sided significance level for the final analysis of primary endpoint (PFS) will be adjusted to account for interim alpha spending so the overall 2-sided significance level for the study will be preserved at 0.05. Tests of secondary endpoints will be performed using the same approach for the interim analysis.

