PFS assessed by IRC	Time from the date of randomization to the date of first IRC-confirmed disease progression (PD) or date of death due to any cause, whichever occurs first, regardless of the use of subsequent antineoplastic therapy prior to documented PD or death. For subjects who do not have IRC-confirmed PD and not known death as of clinical data cutoff, PFS is censored at the date of the last evidence of no progression by IRC.	 The treatment effect of ibrutinib + rituximab (Arm A) compared to placebo + rituximab (Arm B) will be tested with a stratified log rank test adjusted for 2 randomization stratification factors. The hazard ratio and its 95% confidence interval (CI) based on a Cox regression model stratified by the 2 randomization stratification factors will be calculated. Kaplan-Meier analysis for PFS distribution; median PFS estimated with 2-sided 95% CI. Sensitivity Analyses: Subjects who received subsequent antineoplastic therapy are censored at the last disease assessment showing no evidence of PD before the use of subsequent therapy: same analyses as above. Subjects who missed ≥2 consecutively planned disease assessments immediately before IRC-confirmed PD or death are censored at the last disease assessment prior to documented PD or death: same analyses as above. Investigator assessed PFS: same analyses as above. IRC-assessed PFS by unstratified log-rank test and unstratified Cox regression model. 			
Secondary Endpoints					
ORR assessed by IRC	Proportion of subjects achieving a best overall response of confirmed complete response (CR), very good partial response (VGPR), or PR per the IRC assessment at or prior to initiation of subsequent antineoplastic therapy.	ORR will be compared between the two randomized treatment arms (ibrutinib + rituximab vs. placebo + rituximab) using Cochran-Mantel-Haenszel (CMH) chi- square test, adjusted for the 2 randomization stratification factors. 95% CI for the rate ratio will be calculated. Sensitivity Analyses: Investigator assessed ORR: same analyses as above. Subgroup Analyses: Rate ratio and its 95% CI for each subgroup of selected variables (e.g. prior treatment history, MYD88 L265P mutational status).			
Time to next treatment	Time from the date of randomization to the start date of any subsequent WM treatment.	Same as PFS: stratified log-rank test, stratified Cox regression model, and Kaplan-Meier analysis.			

PCYC-1127-CA Statistical Analysis Plan

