Endpoint	Definition	Analysis Methods	
(TTnT)	Subjects without subsequent treatment are censored at the date of the last study visit.		
Rate of sustained hemoglobin improvement	Proportion of subjects achieving a sustained improvement in hemoglobin (Hgb) at or prior to initiation of subsequent antineoplastic therapy. Hgb improvement is defined as an increase of ≥ 2 g/dL over baseline regardless of baseline value, or an increase to >11 g/dL with a ≥ 0.5 g/dL improvement if baseline is ≤ 11 g/dL. Sustained Hgb improvement is defined as improvement that is sustained continuously for ≥ 56 days (8 weeks) without blood transfusion or growth factors.	The two randomized treatment arms will be compared (ibrutinib + rituximab vs. placebo + rituximab) using chi- square test. 95% CI for the rate ratio will be calculated. Subgroup Analysis: Chi-square test for subjects with Hgb ≤ 11 g/dL at baseline.	
Proportion of subjects with ≥ 3 points increase from baseline by Week 25 in fatigue experience score	Proportion of subjects with $a \ge 3$ points increase from baseline in fatigue experience score at any time point at or prior to initiation of subsequent antineoplastic therapy by Week 25. Fatigue experience score is calculated from the FACT-An 5 items (HI7, HI12, An1, An2, An5) assessing fatigue symptoms.	The two randomized treatment arms will be compared (ibrutinib + rituximab vs. placebo + rituximab) using chi- square test. 95% CI for the rate ratio will be calculated.	
Overall survival (OS)	Time from the date of randomization to the date of death from any cause. For subjects who were not known to have died at or prior to the clinical cutoff date, OS is censored on the date last known alive.	Unstratified log-rank test, unstratified Cox regression model, and Kaplan-Meier analysis. Exploratory analysis adjusting the crossover effect may be performed, if needed.	
Exploratory E	ndpoints		
Time to sustained hemoglobin improvement	Time from the date of randomization to the initial date of sustained hemoglobin improvement.	Descriptive summary statistics for subjects who achieved sustained hemoglobin improvement.	
DOR by IRC, DOR by investigator	Time from the date of initial documentation of a response (PR or better) to the date of first documented evidence of PD or death for responders (PR or better). The same censoring rules for PFS are used for DOR.	Kaplan-Meier analysis	

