CRR by IRC, CRR by investigator	Proportion of subjects achieving a best overall response of confirmed CR, VGPR, PR or MR at or prior to initiation of subsequent antineoplastic therapy.	Same analyses as for ORR	

PCYC-1127-CA Statistical Analysis Plan

Page 16 of 18

Endpoint	Definition	Analysis Methods	
IgM, Hgb	Value and change from baseline	Descriptive summary statistics	
Lymph nodes and spleen	Sum of product of diameters for target nodal lesions, spleen depth and spleen volume	Descriptive summary statistics	
Tumor involvement of bone marrow	Cellularity and intertrabecular space	Descriptive summary statistics	
Medical resource utilization	Number of plasmapheresis, number of emergency room visits, number and days of hospitalizations	Descriptive summary statistics	
EQ-5D-5L visual analog scale and utility score, FACT-An total score and subscale scores	Value and change from baseline, proportion of subjects achieving clinically meaningful improvement, time to improvement. Clinically meaningful improvement is defined as an increase of \geq 7 points for visual analog scale (or \geq 0.08 points for utility score, \geq 7 points for FACT-An total score, \geq 6 points for anemia subscale score, \geq 3 points for fatigue subscale score) prior to initiation of subsequent antineoplastic therapy.	Descriptive summary statistics. The proportion of subjects achieving clinically meaningful improvement will be compared between the two randomized treatment arms using chi-square test. 95% CI for the rate ratio will be calculated. For each parameter, change from baseline up to Week 49 will be analyzed using the Mixed-Effects Model Repeated Measure (MMRM). The model includes the baseline scores, baseline ECOG (0, 1-2), prior treatment history on CRF (previously untreated, previously treated), WM IPSS on CRF (low, intermediate, high) as covariates; treatment, time point and treatment-by-time point interaction as fixed effects; and subjects as random effect. An unstructured (co)variance structure will be used to model the within-subject error. Kenward-Roger's approximation will be used to estimate denominator degrees of freedom. The 2-sided 95% CIs will be calculated	

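### The sustained-hemoglobin and fatigue-response tests ignore the baseline value that their own responder rules depend on; the crude chi-square is valid but gives away power

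*SAP*

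**What the plan says.** SAP 1.6 places sustained hemoglobin improvement third and fatigue response fourth in the fixed sequence, after ORR and TTnT and before OS. Once PFS is significant, "tests of secondary endpoints will be performed at the 2-sided significance level of 0.05 in a sequential hierarchical manner".

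For both endpoints SAP Table 2 (section 4.1) gives the same method: "The two randomized treatment arms will be compared (ibrutinib + rituximab vs. placebo + rituximab) using chi- square test", with a 95% CI for the rate ratio. Protocol 10.6.2.2 already had this test for hemoglobin, where the percentage of responders "will be presented and compared using a chi-square test". The fatigue endpoint was added by the SAP (section 5).

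The responder rules are:

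- **Hemoglobin:** a rise of at least 2 "g/dL over baseline regardless of baseline value, or an increase to >11 g/dL with a" gain of at least 0.5 g/dL if baseline is 11 g/dL or lower, sustained for 56 days without transfusion or growth factors.
- **Fatigue:** a rise of at least 3 points at any time by Week 25. "Fatigue experience score is calculated from the FACT-An 5 items", each scored 0 to 4 (protocol 7.1.10.2).

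Elsewhere Table 2 does adjust. PFS and TTnT use stratified log-rank tests, and ORR uses a Cochran-Mantel-Haenszel "chi- square test, adjusted for the 2 randomization stratification factors". The exploratory mixed model for PRO scores includes the baseline score. For hemoglobin, Table 2 also prespecifies a chi-square test in subjects with baseline at or below 11 g/dL, and SAP Table 1 lists that cut as an efficacy subgroup.

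**The concern.** When the chance of response varies strongly with a recorded baseline value, a test that ignores it carries between-subject variation that stratification would remove. The consequence reaches beyond the endpoint itself. In a fixed sequence, a miss on hemoglobin stops formal testing of fatigue and OS, and a miss on fatigue stops OS. The most informative covariate is collected anyway and is used in the exploratory PRO model, but not in the tests that carry alpha. A chance imbalance in baseline also passes unadjusted into the reported rate ratio.

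**Working it through.** **Inputs from the documents.** "A total of 150 subjects were randomized in a 1:1 ratio", taken as 75 per arm; two-sided 0.05; the responder rules above. No response rate, standard deviation, baseline distribution or power is given for either endpoint. Every such value below is an assumption.

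**The plan's own design figure.** It concerns PFS only. Freedman's formula gives (1.96 + 0.8416)² × (1.5/0.5)² = 7.849 × 9 = 70.6, so 71 events, as stated. The interim level of 0.015 also reproduces (0.0151 at 50 of 71 events). Neither bears on these two tests.

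**Dependence on baseline, by definition.**

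- Fatigue: 5 items × 4 = 20 maximum, and 20 − 3 = 17, so a baseline of 18-20 cannot respond.
- Hemoglobin: at baseline 11.0 a rise of 0.5 g/dL suffices; at 11.1 the rise must be 2.0.

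**Chance imbalance.** If half the subjects are at or below 11 g/dL, the between-arm difference in that share has SD √(2 × 0.5 × 0.5/75) = 0.082, about 8 points. Stratifying randomization by IPSS, which counts hemoglobin ≤11.5 g/dL as a factor, would reduce this somewhat.

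**Closed-form check: two equal baseline strata, common odds ratio set so that chi-square power is 65%.** Example with control response 60% (low baseline) and 20% (high), odds ratio 2.55:

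- Treated rates are 79.3% and 38.9%; overall 40.0% against 59.1%, difference 0.191.
- Chi-square: (0.191 − 1.96√(2 × 0.4955 × 0.5045/75)) / √((0.2400 + 0.2417)/75) = (0.191 − 0.160)/0.080 = 0.386, power 65%.
- Stratified: the null variance becomes (2/75) × 0.2096 = 0.00559 and the alternative variance 0.401/75 = 0.00535. (0.191 − 0.1465)/0.0731 = 0.608, power 72.8%.

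| Control response, low / high baseline | Chi-square | Stratified |
|---|---|---|
| 40 / 40% | 65% | 65.0% |
| 50 / 30% | 65% | 66.8% |
| 60 / 20% | 65% | 72.8% |
| 70 / 15% | 65% | 79.9% |
| 70 / 10% | 65% | 84.2% |
| 80 / 5% | 65% | 93.2% |

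The gain runs from nothing to 28 points, depending wholly on the assumed contrast between strata.

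**Fatigue simulation, single visit.** Assumed baseline mean 11, SD 4.5, residual SD 3, effect 1.7 points, 4000 runs:

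| Slope of follow-up on baseline | Chi-square | CMH by baseline quartile | Logistic on baseline |
|---|---|---|---|
| 0.9 | 73.4% | 72.7% | 74.4% |
| 0.7 | 67.6% | 70.3% | 72.4% |
| 0.5 | 58.8% | 67.0% | 70.2% |
| 0.3 | 48.2% | 61.9% | 65.3% |

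With response at any of six visits by Week 25 (slopes 0.8 to 0.4, baseline mean 11 or 13, 1500 runs), CMH by quartile gained from +1 (62.4% to 63.7%) to +17 (57.8% to 74.9%), and logistic adjustment +4 to +21. Two further sets of assumptions with CMH by baseline bands gave +1 to +16 and +1 to +22.

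**Hemoglobin simulation.** CMH at ≤11 against >11 g/dL gained about 0 to +2 points in one mean-shift set and −2 to +6 in another. Where response was assumed to differ strongly by baseline, one set gave +2 to +19. A third set, adjusting for the 11 g/dL cut with or without continuous baseline, gave +1 to +21, most cells +1 to +14.

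**Size.** Simulated null rejection for CMH was 4.7-5.2% (fatigue) and 4.8% (hemoglobin).

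**The case against.** The strongest reply is that nothing here is an error. The crude chi-square is valid under randomization, and its size and interval already allow for chance imbalance. That stands. A reader might infer bias or an inflated type I error from the unadjusted test; neither follows.

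A reader might also attach one figure to the loss, such as 16 points, or treat it as a ceiling. The documents supply no input for that, and the tables show both smaller and larger values. With a large effect there is little to recover: at 75 per arm, assumed rates of 40% against 65% already give the chi-square 87% power, and 40% against 70% give 96%.

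The contrast with ORR is weaker than it looks. ORR is adjusted for two randomization factors, not for the baseline IgM that defines its response. Stratifying by baseline score or hemoglobin is therefore justified by efficiency. It does not by itself restore consistency with ORR.

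The plan is not blind to baseline hemoglobin, given its test and subgroup at 11 g/dL. But that test sits outside the sequence, omits subjects above 11 g/dL and does nothing for fatigue.

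That the protocol specified chi-square for hemoglobin does not settle the matter. Protocol 10.6.2.1 specified it for ORR too, and the SAP moved ORR to CMH.

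**Conclusion.** The point holds as an efficiency loss in two confirmatory tests whose responder rules depend on baseline. Under the assumed inputs, adjustment is worth about +1 to +20 points of power for fatigue: close to zero when follow-up tracks baseline closely (slope 0.9), and near the top when it does not (slope 0.3-0.4). For hemoglobin the gain is about 0 to +5 points under a mean-shift model and larger only if response rates differ strongly by baseline, so the case there is modest. These are ranges under assumptions, not figures or bounds from the plan. The direction is firm for fatigue; the size is not.

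**What to change.** In SAP Table 2:

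- Test fatigue response with CMH stratified by prespecified baseline fatigue-score bands, for example ≤9, 10-14, 15-17 and 18-20. These cuts are illustrative and have no source in the documents.
- Test sustained hemoglobin improvement with CMH stratified by baseline ≤11 against >11 g/dL, the cut the SAP already uses.
- Report the stratified rate ratio with its 95% CI, and keep the crude chi-square as supportive. Do not switch to a logistic odds ratio, which would change the effect measure from the rate ratio the SAP reports.
- Optionally, treat the exploratory PRO responder rates the same way; there, too, "The proportion of subjects achieving clinically meaningful improvement will be compared between the two randomized treatment arms using chi-square test".

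The cost is a few lines of SAP text and code, using data already collected. Two small downsides need a sentence each: subjects with no baseline score need a stated stratum, and the 18-20 band adds no information because nobody in it can respond. Timing matters: the SAP for the final report refers to primary-report analyses already performed. If results are already unblinded, leave the confirmatory test as it is and report the stratified test as a labelled sensitivity analysis.

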8.3.3. Weeks 5-16 (every 4 weeks)

- PK (predose and post-dose) for Arm C ONLY (**Week 5 Only**)
- Continuous daily dosing of study drug (ibrutinib/placebo or open-label ibrutinib)
- PRO assessments (Weeks 5, 9 and 13 Only)
- Symptom-directed Physical Exam
- Eye-related symptom assessment

- Collect blood samples for the following laboratory tests:
 - Hematology
 - Serum chemistry
 - Serum protein electrophoresis (SPEP)
 - Quantitative serum immunoglobulins (IgA, IgG, and IgM)
- Overall Disease Assessment
- Review of AEs and concomitant medications

8.3.4. Week 17

Pre-Dose

- PRO Assessments
- Symptom-directed Physical exam
- Eye-related symptom assessment
- ECOG performance status
- Vitals signs including blood pressure, heart rate, and body temperature
- Collect blood samples for the following laboratory tests:
 - Hematology
 - Serum chemistry
 - Coagulation studies (PT/INR, aPTT)
 - Serum protein electrophoresis (SPEP)
 - Quantitative serum immunoglobulins (IgA, IgG, and IgM)
 - T/B/NK cell counts
 - Predictive biomarkers and mechanisms of resistance
 - CT scan
 - Overall Disease Assessment
- Review of AEs and concomitant medications

Dosing and Post-Dose

- Dispense study drug (ibrutinib/placebo for Arm A and Arm B and open-label ibrutinib for Arm C)
- Administration of study drug
- Administration of rituximab (Arm A and Arm B ONLY)
- Review of AEs and concomitant medications

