CT Scans	x ^k					x ^l					x ^l	x ^m					
Bone Marrow Aspirate ^o and Biopsy ⁿ	x										Weeks 49 and 97 (± 2 weeks)	x	x				
Overall Disease Assessment					x	x				x	x	x	x			x	
Survival Status and new anticancer therapy																	x
Ongoing Subject Assessments																	
Concomitant medications	x		Continuous from Informed Consent to 30 days after last dose of study drug														
Adverse events	x		Continuous from Informed Consent to 30 days after last dose of study drug														
Biomarkers																	
T/B/NK cell counts		x				x									Weeks 33 and 49 Only	x	x
Predictive biomarkers & mechanisms of resistance ^p		x ^q				x									Weeks 33 and 49 Only	x	x

Abbreviations: aPTT=activated partial thromboplastin time; ECG=electrocardiogram; ECOG=Eastern Cooperative Oncology Group; EOT=end-of-treatment; INR=international normalized ration; PD=progressive disease; PO=orally; PRO=patient-reported outcome; PT=prothrombin time; q4 weeks=every 4 weeks; q8 weeks=every 8 weeks; q12 weeks=every 12 weeks

Footnote:

- ^a Rituximab doses may be delayed for up to 3 days due to scheduling conflicts.
- ^b PRO questionnaires should be completed prior to any assessments, and before being clinically evaluated by the study nurse or physician. The questionnaires will be administered at Week 1 and, thereafter PROs will be performed every 4 weeks for the first 6 months, every 8 weeks beginning at Week 25, and thereafter every 16 weeks beginning at Week 49 until disease progression, death, or study end, whichever comes first.

- ^c Following disease progression, every effort should be made to administer the questionnaire every 12 weeks for the first 6 months during the survival follow-up period, unless death or study closure, whichever occurs first.
- ^d Physical Examination includes: general appearance of subject, examination of skin, eyes and fundi, ears, nose, throat, lungs, heart, abdomen, extremities, musculoskeletal system, lymphatic system, and nervous system.
- ^e Only a limited symptom-directed physical examination is required. Review of symptoms should include inquiry of ocular symptoms; subjects should be referred to an ophthalmologist for a formal examination if any Grade ≥ 2 symptoms are reported.
- ^f Women of reproductive potential only. Serum pregnancy test required at Screening and urine pregnancy test required at Day 1 prior to first dose. If the test result is positive, the pregnancy must be ruled out by ultrasound to be eligible.

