2.3. Handling of Missing Data for PRO Analysis

Missing Items within Domains

FACT-An scores are derived per FACT-An Scoring Guidelines (Version 4). Fatigue subscale score is derived per FACIT-Fatigue Subscale Scoring Guidelines (Version 4) from the 13 fatigue related items of FACT-An. Similarly, fatigue experience score is calculated from the 5 items (HI7, HI12, An1, An2, An5) assessing fatigue symptoms and fatigue impact score is calculated from the 8 items (An3-An4, An7-An8, An12, An14-An16) assessing the impact of fatigue.

If there are missing items, subscale scores are prorated. This is done by multiplying the sum of the item scores by the number of items in the subscale, then dividing by the number of items answered. A subscale score is calculated only if >50% of the items were answered. The total score is calculated as the sum of the prorated subscale scores. Total scores are calculated only if the overall item response rate is >80% (i.e. at least 22 of 27 items answered for FACT-G total score, and at least 38 of 47 items answered for FACT-An total score).

3. SUBJECT INFORMATION

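### The ranked fatigue test that gates OS dichotomises an unconfirmed change score with no baseline covariate; it is valid, but under plausible assumptions it gives up much of the available power

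*SAP*

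**What the plan says.** SAP 4.1, Table 2, defines a fatigue responder as a subject with a ≥3 "points increase from baseline in fatigue experience score at any time point at or prior to initiation of subsequent antineoplastic therapy by Week 25". No confirming assessment is asked for. The arms are compared "using chi- square test. 95% CI for the rate ratio will be calculated"; neither the baseline score nor the stratification factors enter the test.

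SAP 2.3 gives the content of the score: "fatigue experience score is calculated from the 5 items (HI7, HI12, An1, An2, An5) assessing fatigue symptoms". Protocol 7.1.10.2 rates each item 0 to 4.

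On timing, Protocol Appendix 1, footnote b, says: "The questionnaires will be administered at Week 1 and, thereafter PROs will be performed every 4 weeks for the first 6 months". With Protocol 8.3.3, 8.3.4, 8.3.6 and 8.3.7, this gives Weeks 5, 9, 13, 17, 21 and 25.

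SAP 1.6 tests the secondary endpoints in fixed order: ORR, TTnT, hemoglobin, fatigue, OS. SAP 5 records the fatigue endpoint as an addition to the protocol's analyses. No expected rate, SD or power is stated for it.

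Two neighbouring rows of Table 2 are handled differently. Hemoglobin improvement must last at least 56 days. For EQ-5D-5L and the FACT-An total and subscale scores, "change from baseline up to Week 49 will be analyzed using the Mixed-Effects Model Repeated Measure (MMRM"), with the baseline score as a covariate.

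**The concern.** One reading 3 points above a single baseline reading makes a responder, and there are six chances. With ordinary questionnaire noise, many subjects whose fatigue has not changed will be labelled improved in both arms. At the other end, a subject who starts at 18, 19 or 20 cannot gain 3 points but stays in the ITT denominator. A test that ignores the baseline score cannot allow for either.

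Two things are at stake. The published improvement rate may be hard to interpret. A real fatigue benefit may also be missed, and under the fixed sequence a miss at step four removes the formal OS test at step five.

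**Working it through.** **The plan's own figure.** The only sizing in the documents is for PFS. Freedman's formula with HR 0.5, two-sided 0.05 and 80% power gives ((1 + 0.5)/(1 − 0.5))² × (1.960 + 0.842)² = 9 × 7.85 = 70.6, so 71 events, as stated. Nothing comparable exists for fatigue, so everything below rests on assumptions.

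**Inputs from the documents.** Score range 5 × 4 = 20; six post-baseline assessments; threshold 3 points; 150 subjects randomized 1:1 (75 per arm taken); two-sided 0.05.

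**Assumed.** True baseline mean 11 and SD 4.5; within-subject error SD σ of 1 to 2.5; true-change SD 2; benefit 1.5 points, reached by Week 13; scores rounded and held within 0–20.

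**Step 1: subjects with no true change.** Rounding puts the effective threshold at 2.5. At a single visit the chance of a false gain is P(Z ≥ 2.5/(σ√2)), which is 4/12/19/24% for σ = 1/1.5/2/2.5. For any of six visits sharing one baseline reading it is 1 − ∫φ(z)Φ(2.5/σ + z)⁶dz = 15/37/50/59%. Simulation with the 0–20 limits gives 4/12/18/23% and 15/35/48/55%. About 9% of subjects start at 18 or above.

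**Step 2: power for a 1.5-point benefit, controls unchanged.** For Week 25 ANCOVA the residual variance is (4.5² + 2² + σ²) − 4.5⁴/(4.5² + σ²). At σ = 1.5 this is 26.5 − 18.2 = 8.3, so the SE is √8.3 × √(2/75) = 0.47 and power is Φ(1.5/0.47 − 1.96) = 89%. The same sum at σ = 1, 2 and 2.5 gives 96, 78 and 66%. The simulated values are a little lower because of the score limits.

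| Power (%) | σ = 1 | 1.5 | 2 | 2.5 |
|---|---|---|---|---|
| Planned any-visit chi-square | 79 | 61–66 | 42–48 | 31–36 |
| Week-25-only responder | 73 | 62 | 46 | 37 |
| Two consecutive visits, unadjusted | 76 | 64–70 | 48–54 | 41–47 |
| Week 25 ANCOVA | 96 (formula) | 86–88 | 73–74 | 63–65 |

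Ranges are over repeat runs of the model. A representative run gives 61/48/35% for the planned test against 86/74/65% for ANCOVA at σ = 1.5/2/2.5. Differences of a few points between rows should not be read.

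**Step 3: where the loss arises.** Going from ANCOVA to a Week-25 responder costs about 24 to 28 points (86 to 62, 74 to 46, 65 to 37). Going from there to the any-visit rule changes little. Over 72 scenarios under a different model (SD 3–5, between-visit correlation 0.5–0.9, baseline mean 10 or 13, effect set for about 80% ANCOVA power), median power was 55% for the planned test, 44% for the Week-25 responder and 78% for ANCOVA. The loss against ANCOVA ran from −3 to 59 points, median 24. The any-visit test was weaker than the Week-25 responder in only 36% of scenarios.

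**Step 4: controls also improve.** Both arms receive rituximab, and Protocol 1.7 cites response rates of 44% and 48% for the extended regimen, so some control improvement is plausible. With a 1.5-point control gain, the planned test falls to 56/37/26% at σ = 1.5/2/2.5; two consecutive visits gives 72/53/42%; ANCOVA stays at 86/73/61%.

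One of the 72 scenarios (mean 10, SD 5, correlation 0.5) shows the saturation. Responder rates of 67% v 80% become 77% v 87% when controls improve. By normal approximation, 0.13/√(2 × 0.735 × 0.265/75) = 1.80, power about 44%; then 0.10/√(2 × 0.82 × 0.18/75) = 1.59, power about 36%. Simulated values are 47% and 31%.

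**Step 5: larger benefits, controls unchanged.** At σ = 1/1.5/2/2.5, planned power is 96/85/69/51% for 2 points and 100/99/95/80% for 3 points.

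**Step 6: type I error.** Simulated at 4.8%.

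**The case against.** The strongest reply is that nothing is invalid. In a randomized, double-blind comparison, noise responders arise equally in both arms under the null, so a reader who infers inflated false-positive risk would be wrong. That stands.

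It is also tempting to blame the any-visit rule for the lost power. Step 3 does not support this: the rule often beats a single-visit responder. It drives the inflated responder rates, not most of the power loss.

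The size is conditional. A 1.5-point benefit is half the SAP's own responder threshold, and no SD, correlation or expected effect is given. That stands too.

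The SAP is less inconsistent than it first looks. Hemoglobin is also tested by an unadjusted chi-square, and the exploratory PRO responder rates are likewise unconfirmed and unadjusted. The 13-item fatigue subscale, which contains these five items plus eight impact items, falls within the planned MMRM. SAP 1 sends further PRO analyses to separate documents. None of this changes the ranked test.

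Finally, replacing the responder rate by a mean difference would change the question asked. A sponsor may prefer to know how many subjects reached a set improvement, so the remedy should keep that form.

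**Conclusion.** The point holds as one of efficiency and interpretability. If error SD is 1.5 to 2.5 points, about 35–55% of unchanged subjects would count as improved. A 1.5-point benefit would be detected with about 61/48/35% power, against 86/74/65% for baseline-adjusted change at Week 25. The causes are dichotomising without a baseline covariate and saturation when controls improve.

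The shortfall matters less at error SD near 1, where the planned test reaches about 79%, or for a 3-point benefit with unchanged controls, where it reaches 80–100%. With between-visit correlation near 0.9 it can vanish.

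A reader might infer that the OS result is lost. The documents do not support that. OS is still estimated, is tested only at study closure, and has no stated power; a miss at any earlier step would block its formal test in the same way. What the fatigue step adds is one avoidable chance of that happening.

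**What to change.** If the data are still blinded, amend the SAP as follows.

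- Keep the responder endpoint and its rank, but require the ≥3-point gain at two consecutive assessments, both by Week 25. This follows the principle of the sustained hemoglobin rule, though visits 4 weeks apart are a shorter span than 56 days.
- Adjust the ranked test for the baseline fatigue experience score, for example by logistic regression on that score, and still report the responder rates.
- State how a missed visit and a subject with no post-baseline score are counted.
- Name the fatigue experience score in the MMRM already planned for the other PRO scores, as a supportive analysis.

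In simulation, baseline adjustment alone changed power by about 0 to +14 points and never lowered it. Adding confirmation took the change to between −3 and +31 points, with the largest gains when controls also improve.

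The cost is SAP wording, with no new data or visits. The downsides are a lower headline responder rate, a few points of power if error is small and controls do not improve, and sensitivity to missed questionnaires.

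The introduction to the final-report SAP refers to analyses already performed for the primary report. If the data are unblinded, leave the ranking and test unchanged and report the adjusted and confirmed versions as labelled sensitivity analyses.
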